Appendix 5. List of High Risk Medications for QTc Prolongation

Antiarrhythmics: Amiodarone; Disopyramide; Dofetilide; Ibutilide; Procainamide; Quinidine; Sotalol.	Miscellaneous: Arsenic; Cisapride; Droperidol; Thioridazine; Pentamidine.
--	--

Adapted from: **Regions Guidelines for Managing Medications and QTc prolongation**. Source: https://cpnp.org/sites/default/files/shared/2013/QTc_Prolongation_Med_Managment_Guideline.doc.

Appendix 6. Alternative Measures During Public Emergencies

The alternative study measures described in this section are to be followed during public emergencies, including the COVID-19 pandemic. This appendix applies for the duration of the COVID-19 pandemic and will become effective for other public emergencies only upon written notification from Pfizer.

These planned changes are being implemented immediately in response to the COVID-19 pandemic and are planned for the duration of the COVID-19 pandemic. This applies to patients who are quarantined or wish to not attend scheduled visits or perform study procedures or tests on site due to safety concerns and/or local government health or health institute suggestions and/or guidelines issued in an effort to limit exposure of vulnerable populations to the virus.

Use of these alternative study measures are expected to cease upon the return of business as usual circumstances (including the lifting of any quarantines and travel bans/advisories).

Eligibility

While SARS-CoV2 testing is not mandated for this study, local clinical practice standards for testing should be followed. A patient should be excluded if he/she has a positive test result for SARS-CoV2 infection, is known to have asymptomatic infection, or is suspected of having SARS-CoV2. Patients with active infections are excluded from study participation as per exclusion criterion # 10: “Active and clinically significant bacterial, fungal, or viral infection, including hepatitis B virus (HBV), hepatitis C virus (HCV), known human immunodeficiency virus (HIV) or acquired immunodeficiency syndrome (AIDS) related illness. In equivocal cases, with positive serology, those patients with a negative viral load are potentially eligible provided the other entry criteria are met.

Telehealth Visits

Study patients who can attend scheduled study visits on site and complete all study procedures as described in the protocol per the Schedule of the Activities should do so; all other participants should make every effort to participate in study visits by telephone via a telehealth visit. Video contact can be used if available and permitted by local regulations.

In the event that in-clinic study visits cannot be conducted, every effort should be made to follow up on the safety of study patients at scheduled visits per the Schedule of Activities or unscheduled visits. Telehealth visits may be used to continue to assess patient safety and collect data points. Telehealth includes the exchange of healthcare information and services via telecommunication technologies (eg, audio, video, video-conferencing software) remotely, allowing the patient and the investigator to communicate on aspects of clinical care, including medical advice, reminders, education, and safety monitoring. The following assessments must be performed during a telehealth visit:

- Review and record study intervention(s), including compliance and missed doses using the protocol required dosing diary.

- Review and record any AEs and SAEs since the last contact. Refer to [Section 8.1](#).
- Review and record any new concomitant medications or changes in concomitant medications since the last contact.
- Review and record contraceptive method and results of pregnancy testing. Confirm that the patient is adhering to the contraception method(s) required in the protocol. Refer to [Section 4.3](#) and the Laboratory Testing section of this appendix regarding pregnancy tests.
- Review of physical symptoms in place of mandated physical exams.

Study patient must be reminded to promptly notify site staff about any change in their health status.

Alternative Facilities for Safety Assessments

If the study participant is unable to visit the study site, protocol specified safety laboratory tests and/or tumor assessments may alternatively be performed at an alternative local laboratory or facility, where allowable by law or local guidance.

Laboratory Testing

If a study patient is unable to visit the site for protocol-specified safety laboratory evaluations, testing may be conducted at a local laboratory if permitted by local regulations. The local laboratory may be a standalone institution or within a hospital. At the discretion of the treating physician home blood draws may be permitted. All safety laboratory tests outlined in this protocol can be done at a local laboratory.

If a local laboratory is used, qualified study site personnel must order, receive, and review results. Site staff must collect the local laboratory reference ranges and certifications/accreditations for filing at the site. Laboratory test results are to be provided to the site staff as soon as possible. The local laboratory reports should be filed in the patient's source documents/medical records. Relevant data from the local laboratory report should be recorded on the CRF.

If a patient requiring pregnancy testing cannot visit a local laboratory for pregnancy testing, a home urine pregnancy testing kit with a sensitivity of at least 25 IU/mL may be used by the patient to perform the test at home, if compliant with local regulatory requirements. The pregnancy test outcome should be documented in the patient's source documents/medical records and relevant data recorded on the CRF. Confirm that the patient is adhering to the contraception method(s) required in the protocol.

Any results that are considered clinically significant must be reported in a timely manner and as directed in the protocol.

Imaging and Efficacy Assessments

If the patient is unable to visit the study site for planned or unplanned imaging assessments the patient may visit an alternative facility to have these assessments performed. Qualified study site personnel must order, receive, and review results and any abnormalities, including progression of disease must be reported to the Pfizer clinical team in a timely manner and as directed in the protocol.

Electrocardiograms

If the patient is unable to visit the study site for ECGs, the patient may visit an alternative facility to have the ECGs performed. Qualified study site personnel must order, receive, and review results.

Study Intervention

If the safety of a trial patient is at risk because they cannot complete required evaluations or adhere to critical mitigation steps, then discontinuing that patient from study intervention must be considered.

PF-06873600 and letrozole may be shipped by courier to study patient if permitted by local regulations and in accordance with storage and transportation requirements for the PF-06873600 and letrozole. Pfizer does not permit the shipment of PF-06873600 and letrozole by mail. The tracking record of shipments and the chain of custody of PF-06873600 and letrozole must be kept in the patient's source documents/medical records.

Pfizer's standard clinical stability studies for small molecule clinical drug products support the temporary lift for the use of temperature monitors if the total duration of ground transportation only from initiation, defined as movement outside of clinical site control, ie, picked up by courier to receipt at final destination is <36 hours. Air transport is not permitted.

Your investigational site must document the shipment process followed (including courier tracking details) and obtain study patient's verbal consent to accept delivery of the study drug at home. Consent is to be documented in the patient medical record.

- Study sites should follow up with the patient once the investigational product is received by the patient to review when to start using the new bottles, the dosing instructions, and completion of the dosing diary/logs.
- Dosing diary/logs should be shipped with the investigational product.
- Upon delivery of study drug, the patient (or caregiver) must communicate the below information back to the site:
 - Description of the state of the package (any physical damage);

- Contents.
 - Number of bottles and lot numbers.
 - Dosing diary/logs.
- Patients should be instructed not to re-use or dispose of any bottles dispensed at a previous visit.
- All bottles and dosing diary/logs must be returned to the study site at the next on-site visit.

The following is recommended for the administration of PF-06873600 for patient who have active [confirmed (positive by regulatory authority-approved test) or presumed (test pending/clinical suspicion)] SARS-CoV2 infection:

- For symptomatic patient with active SARS-CoV2 infection, PF-06873600, letrozole and fulvestrant should be delayed for at least 14 days from the start of symptoms. This delay is intended to allow the resolution of symptoms of SARS-CoV2 infection.
- Prior to restarting treatment, the patient should be afebrile for 72 hours, and SARS-CoV2-related symptoms should have recovered to \leq Grade 1 for a minimum of 72 hours. Notify the study team when treatment is restarted.
- Continue to consider potential drug-drug interactions as described in this protocol for any concomitant medication administered for treatment of SARS-CoV2 infection.

Home Health Visits

A home health care service may be utilized to facilitate scheduled visits per the Schedule of Activities. Home health visits include a healthcare provider conducting an in-person study visit at the patient's location, rather than an in-person study visit at the site. The following may be performed during a home health visit (at the discretion of the treating physician and in consultation with the SPONSOR): scheduled visits per the Schedule of Activities (eg, evaluation of physical symptoms in place of protocol mandated physical examinations, review of adverse events or serious adverse events, dosing compliance, contraception check, and concomitant medication checks, etc.).

Adverse Events and Serious Adverse Events

Study treatment should continue unless the investigator/treating physician is concerned about the safety of the patient, in which case temporary or permanent discontinuation may be required.

It is recommended that the investigator discuss temporary or permanent discontinuation of study intervention with the study medical monitor.

Patient Data Monitoring and Protocol Deviations

Every effort should be made to ensure that required protocol tests and procedures are completed as described with the protocol. However, the circumstances around the ongoing COVID-19 pandemic may make it unfeasible to perform some of the tests and procedures. In these cases, the investigator must take all of the necessary steps to ensure the safety and wellbeing of the study participant. When a required protocol test or procedure cannot be performed, the investigator will promptly document the reason for the missed test or procedure and any corrective and preventive actions they have taken to ensure that required processes will be adhered to as soon as possible. The study team must be informed of these incidents in a timely manner.

Patient data monitoring will continue without interruption. Remote data monitoring will be permitted, wherever possible. The CRA will continue monitoring data in an ongoing manner via remote access following all institutional processes, if applicable.

Any other deviations to the protocol, except for these approved modifications, must be documented as protocol deviations, and if related to the pandemic, the reason should clearly state "COVID-19". These are not immediately required to be reported to health authorities or IRB/ECs unless requested locally.

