In exploratory in vitro genetic toxicity assays, PF-06873600 was not mutagenic or clastogenic, but was observed to be aneugenic. PF-06873600 absorbs light in the 280 nm to 500 nM range with the greatest molar extinction coefficient of 20,643 L/mol•cm at 351 nM, and therefore has the potential to cause phototoxicity. Developmental and reproductive toxicity studies specific for fertility and teratology have not been conducted with PF-06873600 but toxicity to reproductive organs was not observed in the 1-month mouse and dog GLP general toxicity studies. However, based on the mechanism of action, male reproductive and embryo fetal toxicity are potential risks. Adverse effects of other CDK 4/6 inhibitors, including ribociclib, abemaciclib, and palbociclib,^{14,15,34} on male reproductive organs, function and fertility in animal studies were observed and partially reversible in some instances. In addition, effects on fetal growth, survival and morphology were also observed with CDK 4/6 inhibitors in animal studies.

The nonclinical safety findings related to oral administration of PF-06873600 represent toxicities that can be monitored and/or are considered clinically manageable or acceptable risks in the intended advanced cancer patient population.

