4.3. Lifestyle Requirements

In this study, female patients who are of childbearing potential, and fertile male patients as applicable to the study will receive PF-06873600 as a single agent or in combination with endocrine therapy, which currently has unknown teratogenicity/fetotoxicity so must be considered as suspected. Patients who are, in the opinion of the investigator, sexually active and at risk for pregnancy with their partner(s) must agree to use 2 methods of highly effective contraception throughout the study and for at least 28 days after the last dose of PF-06873600. The investigator or his or her designee, in consultation with the patient, will confirm that the patient has selected 2 appropriate methods of contraception for the individual patient (and her partner(s)) from the list of permitted contraception methods (see below) and will confirm that the patient has been instructed in their consistent and correct use. At time points indicated in the Schedule of Activities, the investigator or designee will inform the patient of the need to use 2 highly effective methods of contraception consistently and correctly and document the conversation, and the patient's affirmation, in the patient's chart. In addition, the investigator or designee will instruct the patient to call immediately if 1 or both of the selected contraception methods is discontinued or if pregnancy is known or suspected in the patient or partner.

Highly effective methods of contraception are those that, alone or in combination, result in a failure rate of less than 1% per year when used consistently and correctly (ie, perfect use) and include the following:

1. Established use of hormonal methods of contraception associated with inhibition of ovulation (eg, oral, inserted, injected, implanted, transdermal as approved by local

regulatory authority), provided the patient or male patient's female partner plans to remain on the same treatment throughout the entire study and has been using that hormonal contraceptive for an adequate period of time to ensure effectiveness.

2. Correctly placed copper-containing intrauterine device (IUD).
3. Male condom or female condom used WITH a separate spermicide product (ie, foam, gel, film, cream, or suppository). For countries where spermicide is not available or condom plus spermicide is not accepted as highly effective contraception, this option is not appropriate.

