7.1.1. Pregnancy Testing

All pregnancy tests used in this study, either urine or serum, must have a sensitivity of at least 25 mIU/mL and must be performed by a certified laboratory. For female patients of childbearing potential, 2 negative pregnancy tests are required before receiving PF-06873600 (1 negative pregnancy test at screening and 1 at the baseline visit immediately before PF-06873600 administration). Following a negative pregnancy test result at screening, appropriate contraception must be commenced and the second negative pregnancy test result will then be required at the baseline visit and within 5 days after the first day of the menstrual period (counting the first day of the menstrual period as Day 1) before the patient may receive PF-06873600. In the absence of regular menstrual bleeding, the study candidate should have used 2 forms of contraception for at least 1 month before the second pregnancy test. Pregnancy tests will also be repeated at Day 1 of every other Cycle and at the end of the study to confirm that the patient has not become pregnant during the study. Pregnancy tests will also be done whenever 1 menstrual cycle is missed during the active treatment period and when potential pregnancy is otherwise suspected, and may be repeated if requested by institutional review boards (IRBs)/ethics committees (ECs) or if required by local

regulations. In the case of a positive confirmed pregnancy, the patient will be withdrawn from administration of investigational product and from the study.

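### Appendix 6 states the home pregnancy-kit sensitivity in IU/mL and the rest of the protocol uses mIU/mL: an unexplained 1000-fold inconsistency, minor and probably a unit slip

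*Protocol*

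**What the plan says.** Three places in the current protocol give a sensitivity figure for pregnancy tests.

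- **Section 7.1.1, Pregnancy Testing:** "All pregnancy tests used in this study, either urine or serum, must have a sensitivity of at least 25 mIU/mL". The same sentence adds that the tests are to be done by a certified laboratory.
- **Appendix 7.1, item 11 (Japan):** the same requirement, with the same number and unit.
- **Appendix 6, Laboratory Testing:** where a patient who needs pregnancy testing cannot go to a local laboratory, "a home urine pregnancy testing kit with a sensitivity of at least 25 IU/mL may be used by the patient", provided that this complies with local regulatory requirements.

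On scope, Appendix 6 says "This appendix applies for the duration of the COVID-19 pandemic"; for other public emergencies it needs written notice from the sponsor. Its list of tasks for telehealth visits includes reviewing pregnancy test results, and for those tests it refers staff to its own Laboratory Testing text and not to Section 7.1.1.

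On risk, Section 4.3 describes study treatment as something "which currently has unknown teratogenicity/fetotoxicity so must be considered as suspected", and Section 1.3.3 states that "based on the mechanism of action, male reproductive and embryo fetal toxicity are potential risks".

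**The concern.** The number in the appendix matches the one in the main text, but the unit does not. Read literally, the appendix accepts a home kit that need only detect a concentration 1000 times higher than the one required everywhere else.

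This is an acceptance limit in working instructions, not background text. A site arranging home testing would look in Appendix 6, because the telehealth instructions point there. The same passage openly departs from Section 7.1.1 on another matter, since it allows testing at home instead of in a certified laboratory. A careful reader could therefore take the different sensitivity figure as part of the same exception. Appendix 6 also exempts its own approved modifications from deviation documentation, so a kit that met only the appendix figure might never be flagged.

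What is at stake is patient safety, not inference. A confirmed pregnancy leads to withdrawal from investigational product and from the study (Section 7.1.1), and Appendix 6 allows oral study drug to be couriered to patients at home. The home result may then be the only scheduled check while dosing continues.

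**Working it through.** **Inputs**

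| Place | Limit as written | Applies to |
|---|---|---|
| Section 7.1.1 | 25 mIU/mL | all tests, urine or serum |
| Appendix 7.1, item 11 | 25 mIU/mL | all tests, urine or serum (Japan) |
| Appendix 6, Laboratory Testing | 25 IU/mL | home urine kit, public emergency |

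The protocol gives no derivation for either figure, so there is nothing to reproduce beyond the unit conversion. I read sensitivity in all three places as the concentration that the test must be able to detect.

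**Step 1, common unit.** 1 IU = 1000 mIU, so 25 IU/mL × 1000 = 25,000 mIU/mL.

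**Step 2, ratio.** 25,000 ÷ 25 = 1000. With a shared unit the ratio would be 25 ÷ 25 = 1.

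**Step 3, can one kit satisfy both texts?** Yes. A kit that detects 25 mIU/mL meets both. A kit that detects only 25 IU/mL meets Appendix 6 and fails Section 7.1.1. The texts conflict only over kits between those two figures.

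**Step 4, is a different limit explained?** No. Appendix 6 gives reasons for testing away from the site, but none for a different sensitivity.

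**Step 5, time to the next scheduled test.** Section 7.1.1 schedules tests on Day 1 of every other cycle, and a cycle is 28 days: 2 × 28 = 56 days. A falsely negative scheduled test could therefore stand for about 56 days, unless a missed menstrual cycle or other suspicion of pregnancy prompted an unscheduled one.

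**Step 6, how long the text still matters.** Amendment 9 is dated 03 March 2023 and Section 13.2 puts primary completion on or around 5 April 2023. After that, Section 7 moves safety procedures to local standard of care. The schedule of activities following Amendment 9 lists only PF-06873600, fulvestrant and adverse event reporting. No scheduled pregnancy test is left for a home kit to replace.

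**The case against.** The strongest reply is that this is an editorial slip with almost no practical reach.

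- **Intent.** Number and phrasing match; only the prefix differs. Nothing suggests a deliberate relaxation. This stands.
- **Study-wide rule.** Section 7.1.1 covers every test, and a home urine kit is one. This narrows the conflict but does not remove it, because Appendix 6 already overrides the certified-laboratory half of the same sentence and staff are directed to the appendix.
- **Other safeguards.** Kits must comply with local regulatory requirements. Screening uses a serum test. Women of childbearing potential with HR-positive HER2-negative disease, the population of every Part 2 arm, must have medically induced menopause. Patients at risk of pregnancy use two contraceptive methods, which are reviewed at telehealth visits. Extra tests follow a missed menstrual cycle or any suspicion of pregnancy. All of this stands and lowers the risk, although the induced-menopause rule does not cover the triple-negative and ovarian patients in Parts 1A and 1C.
- **Timing.** The measure is confined to emergencies, and scheduled testing drops out after primary completion. This stands, and it makes the point largely retrospective.

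A reader might infer that pregnancies were missed, or that sites handed out inadequate kits. The documents support neither. They do not say which kits were used, whether anyone supplied them, or whether a kit with a limit of 25 IU/mL would have been accepted anywhere. The factor of 1000 compares two written limits; it does not measure lost detection.

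**Conclusion.** This is a genuine internal inconsistency in current text, of minor severity. Two places set 25 mIU/mL and one sets 25 IU/mL, a 1000-fold difference that the protocol does not explain. It is probably a unit slip, and it should not be read as a design decision to loosen fetal-safety monitoring.

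It is worth raising because the odd figure sits where staff are sent for instructions, the protocol treats fetal harm as suspected, and reconciling it costs little. Its reach is limited to patients who need pregnancy testing and cannot visit a local laboratory during a public emergency, using kits that also comply with local regulatory requirements. No endpoint, estimate, sample size or analysis depends on it.

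The conclusion assumes that the units in the source PDF are as they appear in the text. The prefix is intact in Section 7.1.1 and Appendix 7.1, which makes a reading error in Appendix 6 less likely, but the page should be checked.

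**What to change.** The sponsor should reconcile Section 7.1.1, Appendix 6 (Laboratory Testing) and Appendix 7.1 item 11 so that a single sensitivity limit, in a single unit, applies to laboratory and home tests. If a different limit for home kits is intended, Appendix 6 should say so and give the reason. Which limit applies is for the sponsor to decide.

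Sites should be asked whether any home kits were used under Appendix 6 and, if so, to check them against the reconciled limit.

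The cost is a short text correction and a note to sites. No data collection, analysis or SAP text changes.
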